8.5 Changes to the protocol and informed consent form

Study procedures will not be changed without the mutual agreement of the Investigator and AstraZeneca.

If there are any substantial changes to the CSP, these changes will be documented in a CSP amendment and, where required, in a new version of the CSP (Revised Protocol).

The amendment should be approved by the Ethics Committee and if applicable, also the national regulatory authority, before implementation. Local requirements should be followed for revised protocols.

AstraZeneca will distribute any subsequent amendments and new versions of the protocol to the Investigator. For distribution to the Ethics Committee see Section 8.3.

If a protocol amendment requires a change to the Informed Consent Form, AstraZeneca and the Ethics Committee should approve the revised Informed Consent Form before the revised form is used.

If local regulations require, any administrative change will be communicated to or approved by the Ethics Committee.

8.6 Audits and inspections

Authorized representatives of AstraZeneca, a regulatory authority, or an Ethics Committee may perform audits or inspections at the center, including source data verification. The purpose of an audit or inspection is to systematically and independently examine all study-related activities and documents, to determine whether these activities were conducted, and data were recorded, analyzed, and accurately reported according to the CSP, ICH/GCP guidelines, and any applicable regulatory requirements. The Investigator will contact AstraZeneca immediately if contacted by a regulatory agency about an inspection at the center.

9. STUDY MANAGEMENT

9.1 Prestudy activities

Before the first volunteer is entered into the study, it is necessary for a representative of AstraZeneca to visit the investigational study site to:

- Determine the adequacy of the facilities
- Determine availability of appropriate volunteers for the study
- Discuss with the Investigator(s) (and other personnel involved with the study) their responsibilities with regard to protocol adherence and the responsibilities of AstraZeneca or their representatives.

9.2 Training of study site personnel

Before the first volunteer is entered into the study, an AstraZeneca representative will review and discuss the requirements of the CSP and related documents with the investigational staff and also train them in any study-specific procedures.

The Investigator will ensure that appropriate training relevant to the study is given to all of these staff and that any new information relevant to the performance of this study is forwarded to the staff involved.

The Investigator will maintain a record of all individuals involved in the study (medical, nursing, and other staff).

9.3 Monitoring of the study

During the study, an AstraZeneca representative will have regular contacts with the study site, including visits to:

- Provide information and support to the Investigator
- Confirm that facilities remain acceptable
- Confirm that the investigational team is adhering to the CSP, that data are being accurately and timely recorded in the CRFs, that biological samples are handled in accordance with the Laboratory Manual, and that study drug accountability checks are being performed
- Perform source data verification (a comparison of the data in the CRFs with the volunteer's medical records at the hospital or practice, and other records relevant to the study) including verification of informed consent of participating volunteers. This will require direct access to all original records for each volunteer (eg, clinic charts).
- Ensure withdrawal of informed consent to the use of the volunteer's biological samples is reported and biological samples are identified and disposed of/destroyed accordingly, and the action is documented and reported to the volunteer

The AstraZeneca representative will be available between visits if the Investigator(s) or other staff at the center need information and advice about the study conduct.

9.3.1 Source data

The location of data identified as source will be provided in a source data identification document provided by .

9.4 Study agreements

The Investigator should comply with all the terms, conditions, and obligations of the CSA or equivalent for this study. In the event of any inconsistency between this CSP and the CSA, the CSP shall prevail with respect to the conduct of the study and the treatment of volunteers and in all other respects, the terms of the CSA shall prevail.

Agreements between AstraZeneca and the Investigator should be in place before any study-related procedures can take place or volunteers are enrolled.

9.4.1 Archiving of study documents

The Investigator follows the principles outlined in the CSA.

9.5 Study timetable and end of study

The end of the study is defined as 'the last visit of the last volunteer undergoing the study'.

The study is expected to start in Q1 2012 and to end by Q3 2012.

The study may be terminated if the study procedures are not being performed according to GCP, or if recruitment is slow. AstraZeneca may also terminate the entire study prematurely if concerns for safety arise within this study or in any other study with ceftaroline fosamil.

10. DATA MANAGEMENT

Data management will be performed by

The data in this study will be collected using paper CRFs.

When the completed paper CRF have been scanned and indexed, the data are entered into the study database and proofread.

The data collected through third party sources will be obtained and reconciled against study data.

Adverse events and medical/surgical history will be classified according to the terminology of the latest version the Medical Dictionary for Regulatory Activities (MedDRA). Medications will be classified according to the AstraZeneca Drug Dictionary. All coding will be performed by

Data queries will be raised for inconsistent, impossible or missing data. All entries to the study database will be available in an audit trail.

The data will be validated as defined in the Data Management Plan. Quality control procedures will be applied to each stage of data handling to ensure that all data are reliable and have been processed correctly.

When all data have been coded, validated and signed the database will be locked.

Data associated with biological samples will be transferred to laboratories internal or external to AstraZeneca as described in the Laboratory Manual.

11. EVALUATION AND CALCULATION OF VARIABLES

11.1 Calculation or derivation of safety variable(s)

11.1.1 Calculation of change from baseline

Change-from-baseline values will be calculated for the variables listed below, as the posttreatment value minus the value at baseline. The baseline values for both Part A and Part B will be as follows:

- Clinical laboratory tests: Day -1

- Vital signs (supine): Day 1 predose

If a volunteer is missing the baseline collection, the previous nonmissing evaluation will become the baseline value. If no baseline or previous-to-baseline value exist, then the baseline value will be treated as missing and no changes from baseline will be calculated.

11.1.2 Other significant adverse events

During the evaluation of the AE data, an AstraZeneca medically qualified expert will review the list of AEs that were not reported as SAEs or AEs leading to discontinuation of IP and withdrawal from the study. Based on the expert's judgement, significant AEs of particular clinical importance may, after consultation with the Global Safety Physician, be considered OAEs and reported as such in the CSR. A similar review of other data from laboratory tests, vital signs, ECGs, and other safety assessments will be performed for identification of OAEs.

Examples of these are marked hematological and other laboratory abnormalities, certain events that lead to intervention (other than those already classified as serious), dose reduction, or significant additional treatment.

11.2 Calculation or derivation of pharmacokinetic variables

Pharmacokinetic analysis of the plasma concentration data for ceftriaxone fosamil (the prodrug of ceftriaxone), ceftriaxone, and ceftriaxone M-1 (the metabolite of ceftriaxone) will be performed at . Standard Operating Procedures and Work Instructions will be used as the default methodology if not otherwise specified. The actual sampling times (in unit of hour) will be used in the PK parameter calculations. In addition, for the purpose of calculating time deviations and graphical presentations of the concentration versus time profiles, the nominal time will be converted to units of hour for PK protocol time points that are in units of minute (including 20-, 40-, 60-, 65-, 75-, and 90-minute plasma PK samples). These derived nominal time points will be rounded to 2 decimal places.

Pharmacokinetic parameters will be derived using noncompartmental methods with WinNonlin[®] Professional Version 5.2, or higher, (Pharsight Corp., Mountain View, California, US) or SAS[®] Version 9.2, or higher (SAS Institute Inc., Cary, North Carolina, US). All PK computations will be performed using WinNonlin[®] Professional Version 5.2, or higher; or SAS[®] Version 9.2, or higher. Graphics may be prepared with SAS[®] Version 9.2, or higher; or SigmaPlot[®] 9.0, or higher (Systat Software Inc., San Jose, California, US).

Where estimable, the following single-dose PK parameters will be calculated for ceftriaxone fosamil, ceftriaxone, and ceftriaxone M-1 from plasma concentrations collected following dosing in each period (Days 1 and 3):

- Maximum plasma concentration (C_{max} , $\mu\text{g/mL}$), obtained directly from the observed concentration versus time data

- Time to maximum concentration (t_{\max} , h), obtained directly from the observed concentration versus time data
- Area under the plasma concentration-time curve from zero to infinity (AUC, $\mu\text{g}\cdot\text{h}/\text{mL}$), calculated by linear up/log down trapezoidal summation and extrapolated to infinity by addition of the last quantifiable concentration divided by the elimination rate constant: $\text{AUC}_{(0-t)} + C_{\text{last}}/\lambda_z$. If the extrapolated area ($C_{\text{last}}/\lambda_z$) is greater than 20% of AUC, then AUC and related parameters will be not reported.
- Area under the plasma concentration-time curve from zero to time of the last quantifiable concentrations ($\text{AUC}_{(0-t)}$, $\mu\text{g}\cdot\text{h}/\text{mL}$)
- Area under the plasma concentration-time curve from zero to 12 hours after the start of the infusion ($\text{AUC}_{(0-12)}$, $\mu\text{g}\cdot\text{h}/\text{mL}$)
- Apparent terminal elimination rate constant (λ_z , 1/h)
- Half-life associated with the terminal slope ($t_{1/2\lambda_z}$, h), determined as $\ln(2)/\lambda_z$
- Mean residence time (MRT, h)
- Total body clearance of drug from plasma (CL, L/h) (for ceftaroline fosamil and ceftaroline [apparent CL])
- Volume of distribution based on the terminal phase (V_z , L) (for ceftaroline fosamil and ceftaroline [apparent V_z])
- Volume of distribution at steady state (V_{ss} , L) calculated as the product of MRT and CL for nonsteady-state data (for ceftaroline fosamil and ceftaroline [apparent V_{ss}])
- C_{\max} ratios of ceftaroline/ceftaroline fosamil and ceftaroline M-1/ceftaroline ($R_{\text{M/D},C_{\max}}$) (adjusted for differences in molecular weights)
- AUC ratios of ceftaroline/ceftaroline fosamil and ceftaroline M-1/ceftaroline ($R_{\text{M/D},\text{AUC}}$) (adjusted for differences in molecular weights)

The molecular weights to be applied in the PK calculations are 684.7 for ceftaroline fosamil, 604.7 for ceftaroline and 622.7 for ceftaroline M-1.

Individual ratios of Treatment A/Treatment C (or Treatment E/Treatment C, if applicable) will also be calculated for ceftaroline AUC, $\text{AUC}_{(0-t)}$, $\text{AUC}_{(0-12)}$, and C_{\max} .

The following PK parameters will be calculated for diagnostic purposes and will be listed, but not summarized:

- The time interval (λ_z upper and lower) of the log-linear regression to determine $t_{1/2\lambda_z}$

- Number of data points (λ_z , N) included in the log-linear regression analysis
- Goodness-of-fit statistic for calculation of λ_z (Rsqr)
- The percent of AUC which is extrapolated to infinity (AUC_{ex} , %)

A minimum of 3 data points and an Rsqr value of >0.8 will be used as the criteria for reliable estimation of λ_z .

Due to collection of a blood sample at the end of the infusion, no additional calculation of a concentration at the end of infusion will be performed. The decision to impute a missing end-of-infusion value, or if there is a large time deviation associated with the end-of-infusion sample, will be made on a case-by-case basis per Standard Operating Procedures and Work Instructions. The approach applied in the analyses will be documented in the CSR.

11.3 Calculation or derivation of pharmacodynamic variable(s) (Not applicable)

12. STATISTICAL METHODS AND SAMPLE SIZE DETERMINATION

12.1 Description of analysis sets

12.1.1 General principles

The analysis of data will be based on different subsets according to the purpose of analysis, ie, for safety and PK, respectively. The decision regarding validity of data for each of the analysis sets will be based on a blind review of data.

The as-treated principle will be applied to all evaluations, ie, volunteers who receive treatment other than the one designated in the randomization schedule will be analyzed by actual treatment and not by randomized treatment.

12.1.2 Analysis of safety population

All volunteers who receive at least 1 dose of randomized IP, ceftriaxone fosamil or placebo, and for whom any postdose data are available, will be included in the safety population.

12.1.3 Pharmacokinetics analysis set

The PK analysis set will include all volunteers who receive at least 1 dose of ceftriaxone fosamil and have at least 1 measured concentration of any of the 3 analytes in plasma at a scheduled time point after the start of the infusion. The PK analysis set should include all evaluable data appropriate for the evaluation of interest (with no major protocol deviations or violations thought to significantly affect the PK of the IP) from all volunteers who received IP.

12.2 Methods of statistical analyses

12.2.1 General principles

Given the exploratory nature, no formal statistical hypothesis testing will be performed in this study. Standard Operating Procedures and Work Instructions will be used as the default methodology if not otherwise specified.

Missing data will result in a reduced sample size for that parameter. Since the statistical analyses will be predominantly presentations in tables and individual data listings, no action will be taken to handle missing data.

A volunteer who withdraws prior to the last planned observation in a study period will be included in the analyses up to the time of discontinuation.

Results from both Part A and Part B will included in the clinical study report.

12.2.2 Subject characteristics

Continuous variables will be summarized using descriptive statistics (n, mean, standard deviation [SD], minimum, median, and maximum). Categorical variables will be summarized in frequency tables (frequency and proportion). Tabular summaries will be presented for all Part A and Part B volunteers overall.

12.2.3 Safety and tolerability

Continuous variables (clinical chemistry, hematology, and vital signs) will be summarized using descriptive statistics (n, mean, SD, minimum, median, and maximum) by scheduled time point. Categorical variables (AEs and urinalysis) will be summarized in frequency tables (frequency and proportion).

For Part A, systemic AEs will be summarized by the active treatment received in the respective treatment period (ie, ceftaroline fosamil 600 mg in either 50 or 250 mL infusion volumes). Clinical laboratory and vital sign parameters will be summarized by scheduled assessment (Day -1 to follow-up) for all Part A volunteers overall.

For Part B, AEs will be presented by treatment (ie, ceftaroline fosamil 600 mg in 50, 100, or 250 mL infusion volumes, as applicable). Clinical laboratory and vital sign parameters will be summarized by scheduled assessment (Day -1 to follow-up) for all Part B volunteers overall.

SAEs will be collected from the time when informed consent is signed until the follow-up visit. Non-serious AEs will be collected from Day -1 (first admission period) until the follow-up visit. Adverse events that occur before the first dose of IP will be listed and flagged, but will not be included in the tabular summaries of AEs.

Adverse events will be presented by preferred term and system organ class according to MedDRA classification. Listings of SAEs and AEs that led to withdrawal will be presented and the number of volunteers who had any AEs, SAEs, AEs that led to withdrawal, AEs

judged as causally related to IP by the Investigator, and AEs with severe intensity will be summarized.

Electrocardiogram and physical examination findings will be listed only.

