2.2 Secondary objectives

The secondary objective of Part A of the study is to evaluate the safety of ceftaroline in healthy volunteers when ceftaroline fosamil 600 mg is diluted in various infusion volumes and infused into the same vein over 60 minutes every 12 hours for 72 hours (6 infusions).

The secondary objectives of Part B are:

- To characterize the PK of ceftaroline fosamil (the prodrug of ceftaroline) and ceftaroline M-1 (the microbiologically inactive metabolite of ceftaroline) in healthy volunteers following a single-dose administration of ceftaroline fosamil 600 mg diluted in various infusion volumes and infused over 60 minutes
- To evaluate the safety and tolerability of ceftaroline in healthy volunteers following a single-dose administration of ceftaroline fosamil 600 mg diluted in various infusion volumes and infused over 60 minutes

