5.5.2 Doses and treatment regimens

During Part A, each volunteer will receive simultaneous bilateral iv infusions of IP (ceftaroline fosamil 600 mg in 1 arm and placebo in the other arm) over 60 minutes every 12 hours for a maximum of 72 hours (6 infusions). Volunteers will then enter a minimum 4.5-day (approximately 108 hours) washout period before crossing over and receiving simultaneous bilateral iv infusions of IP (ceftaroline fosamil 600 mg in the contralateral arm from Period 1 and placebo in the other arm), in veins different than those used previously, over 60 minutes every 12 hours for a maximum of 72 hours (6 infusions). Should the volunteer experience an ISR of 2 or greater as measured by the Visual Infusion Phlebitis (VIP) scale (see [Appendix D](#)), the infusion must be stopped on that arm (ie, the cannula will not be resited for that treatment period) and the ISR will be recorded as an AE. The infusion on the other arm will continue, as appropriate. See Section [5.8](#) for study stopping criteria and Section [3.1.1](#) for a description of treatments and treatment sequences.

In Part B, each volunteer will receive a single dose of 600 mg ceftaroline fosamil infused over 60 minutes in each crossover period (Days 1 and 3). See Section [3.1.2](#) for a description of treatments.

Catheters should be standardized and approved for use in both the US and EU. For each crossover portion, catheters should be inserted into the same ‘anatomical site’, preferably hand and forearm, with care taken to minimize cannula placement in the wrist or antecubital fossa.

Cannula insertion must be performed by a qualified health care professional. Aseptic technique must be used and standard precautions observed prior to and during vascular access placement. This includes the appropriate use of hand hygiene, glove selection, glove use, and decontamination of the peripheral catheter site with individually packaged alcohol wipes. Please note, only alcohol wipes are to be used to clean the site of catheter placement. Peripheral vascular access catheter placement will be documented for each volunteer in a separate source document. Information recorded will include batch number, gauge and length, number of attempts, anatomical location, and volunteer's response to placement. Care of the catheter site and restrictions are specified in advance. The mechanics of line clearance post infusion should be carefully considered.

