For dosing in both study parts and for all infusions, the date and time of the infusion start and stop as well as the start and stop of any infusion interruption and restart of the infusion, and the actual volume and amount of ceftaroline fosamil infused will be recorded. In addition, the arm (left or right) in which the infusion is administered will be documented.

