5.8 Discontinuation of investigational product and withdrawal from study

Volunteers may be discontinued from IP in the following situations:

- Volunteer decision. The volunteer is at any time free to discontinue treatment, without prejudice to further treatment.
- Adverse event
- Severe noncompliance to this CSP as judged by the Investigator and/or AstraZeneca
- Randomization in error (see Section 5.3)
- Catheter becomes dislodged or is removed from either arm prior to scheduled time point

Dosing for any individual volunteer will be stopped if the volunteer experiences a possibly drug-related SAE or a possibly drug-related significant nonserious AE, which in the opinion of the Investigator or Sponsor, warrants discontinuation from the study for that volunteer's well being.

Volunteers who have a VIP score of 2 or more will not have any further infusions in the affected arm for that treatment period. For Part A, if the infusion site in the contralateral arm is healthy, the infusions may continue in that arm.

Stopping criteria for Part A

Dosing will stop with an infusion volume (50, 100 or 250 mL) if any of the following scenarios occur with a reasonable possibility of a causal relationship with the investigational product:

- Two or more subjects report a serious adverse event (SAE) or have a VIP score of 5
- Four or more subjects have a VIP score of 4

During Part A of the study data will be reviewed by the Investigator on an ongoing basis. If 15 or more subjects develop ISRs, but the stopping criteria listed above have not been met, the Investigator may request an independent unblinded review of the available safety and tolerability data. If once unblinded the incidence of ISRs on any active volume is >40% of the total anticipated recruitment for Part A, an ad hoc data review meeting will be arranged between the Investigator, Sponsor, and other team members, as applicable, to determine study termination. Otherwise, dosing will be continued as planned in the remaining 50 mL subjects.

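### Part A shows systemic AEs only as crude incidence by active volume, although the VIP stopping rule cuts active dosing short more often on a more irritating volume

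*Supplement*

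**What the plan says.** Each Part A period plans six simultaneous bilateral infusions, with "ceftaroline fosamil 600 mg in 1 arm and placebo in the other arm" (Section 5.5.2). Section 5.8 sets the arm-level rule: "Volunteers who have a VIP score of 2 or more will not have any further infusions in the affected arm for that treatment period". Section 5.5.2 adds that "the cannula will not be resited for that treatment period", and Section 5.8 that "if the infusion site in the contralateral arm is healthy, the infusions may continue in that arm". When the affected arm is the active one, the volunteer can therefore finish the period on placebo alone.

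Section 12.2.3 says that categorical safety variables, AEs among them, "will be summarized in frequency tables (frequency and proportion"), and that in Part A "systemic AEs will be summarized by the active treatment received in the respective treatment period". The volumes it then names are 50 and 250 mL. One dose and any postdose data are enough for the safety population (Section 12.1.2). Section 5.5.2 requires that "the actual volume and amount of ceftaroline fosamil infused will be recorded", but Section 12 plans no table of it and no AE rate by exposure.

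The secondary objective of Part A (Section 2.2) is safety when the drug is "infused into the same vein over 60 minutes every 12 hours for 72 hours (6 infusions").

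**The concern.** The amount of active drug a volunteer receives in a period depends on whether an ISR occurs, and ISR frequency is what is expected to differ by volume. Section 5.8 plans explicitly for more than 40% on active 50 mL with 40% or less on active 250 mL. In that case the 50 mL column of the systemic AE table would describe volunteers who had, on average, fewer active infusions than those in the 250 mL column. A volunteer given one active infusion counts the same as one given six.

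If systemic AE risk rises with the number of active infusions, the more irritating volume will look somewhat better systemically than six infusions of it would. Nothing else planned in Section 12 would reveal this. Laboratory and vital-sign data are pooled over all Part A volunteers, and ECG and physical examination findings are only listed. The AE table is thus the only by-volume summary of systemic safety in Part A.

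**Working it through.** The plan gives no figure for expected exposure or systemic AE risk, so there is nothing of its own to reproduce. The check asks how large the distortion could be.

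**Inputs from the protocol.** Six planned active infusions per period, 12 hours apart (5.5.2); about 32 volunteers, each due to receive both active volumes (5.2, 12.3); an ISR threshold of 40% (5.8); infusion-site AEs in 2 of 8 = 25% on multiple doses in 250 mL, and in 44% in 140 mL (1.3).

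**Assumptions.** ISR rates on the more and less irritating volume of 40% or 60% against 25% or 10%. The same systemic AE risk per active infusion in both volumes, q, set so that six infusions give 20%: q = 1 − 0.80^(1/6) = 0.0365. The infusion at which the ISR appears counts as received.

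**Onset (a), constant hazard.** For cumulative ISR rate c, h = 1 − (1 − c)^(1/6). Mean active infusions = Σ(1 − h)^(j−1) over j = 1 to 6 = c/h.
- c = 10%: h = 0.0174, mean 5.75
- c = 25%: h = 0.0468, mean 5.34
- c = 40%: h = 0.0816, mean 4.90
- c = 60%: h = 0.1416, mean 4.24

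Crude AE incidence = Σ P(k infusions received) × [1 − (1 − q)^k].

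**Onset (b), all ISRs at infusion 1.** Mean = c × 1 + (1 − c) × 6. Crude incidence = c × q + (1 − c) × 0.20. For 60% this is 0.6 × 0.0365 + 0.4 × 0.20 = 0.102; for 10%, 0.1 × 0.0365 + 0.9 × 0.20 = 0.184. The gap is 0.082 × 32 = 2.6 subjects.

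| ISR rates | (a) exposure ratio | (a) crude AE | (a) gap of 32 | (b) exposure ratio | (b) crude AE | (b) gap of 32 |
|---|---|---|---|---|---|---|
| 40% v 25% | 0.92 | 16.5% v 17.9% | 0.5 | 0.84 | 13.5% v 15.9% | 0.8 |
| 40% v 10% | 0.85 | 16.5% v 19.2% | 0.9 | 0.73 | 13.5% v 18.4% | 1.6 |
| 60% v 25% | 0.79 | 14.4% v 17.9% | 1.1 | 0.63 | 10.2% v 15.9% | 1.8 |
| 60% v 10% | 0.74 | 14.4% v 19.2% | 1.5 | 0.55 | 10.2% v 18.4% | 2.6 |
| 25% v 25% | 1.00 | equal | 0 | 1.00 | equal | 0 |

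**Sensitivity to the AE risk.** The gap scales roughly with it. Under (a), 10% over six infusions gives 8.2% v 8.9% (0.2 subjects) at 40% v 25%, and 7.1% v 9.6% (0.8) at 60% v 10%. With 30% it gives 24.9% v 26.9% (0.7) and 21.7% v 28.8% (2.3).

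**Cross-check with another onset model.** Take 5% risk per infusion. With onset spread evenly over infusions 1 to 6, mean infusions = 6 − 2.5c: 5.0 v 5.4 at 40% v 25%, and incidence 22.3% v 23.9%. With onset at infusions 1 or 2, mean = 6 − 4.5c: 3.3 v 4.9 at 60% v 25%, and incidence 15.0% v 21.7%. The direction and order of size are the same.

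**Does an exposure-based rate help?** Under (a), incidence divided by mean active infusions is 0.0336 v 0.0335 at 40% v 25%, and 0.0339 v 0.0334 at 60% v 10%. The difference almost vanishes, but the model assumes constant risk per infusion, so this shows consistency and does not validate the rate.

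**The case against.** The strongest reply is that this is a small caveat on a descriptive, secondary table.

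- Section 12.2.1 rules out formal testing, and the quantified rules in Section 5.8 use ISR incidence, VIP scores and SAE counts. A reader might infer that the decision on 50 or 100 mL, or the ISR result, is biased; the text does not support that. This stands.
- The upper end is speculative. At 60%, about 19 of 32 volunteers would have ISRs on one volume, past the 15-subject point in Section 5.8 at which an unblinded review may be requested, so full dosing cannot be taken for granted. The 25% prior counts any mild infusion-site AE, not VIP 2 or more. A gap of 15% v 22% is below one standard error of a difference at 32 per volume (about 10 points, treating the volumes as independent). This stands too.
- Crude incidence is a usual Phase I display and correctly describes a volume as used under this stopping rule. A rate per infusion fits first-dose reactions and background events poorly. Both points stand, and they are why crude incidence should remain the main display.
- No SAP is shown, and exposure tables are often specified there. The absence of one from Section 12 does not prove that none is planned. But Section 12.2.3 does define the AE summary, and the missing-data and withdrawal rules in Section 12.2.1 do not cover an arm-level stop.
- A patient reader could piece together early stops and late AEs from the listings. That is possible for 24 to 32 volunteers, but it does not replace a table.

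A reader might also infer that Treatment E would drop out of the systemic AE summary because only 50 and 250 mL are named. The governing phrase is the active treatment given, which covers Treatment E; Section 12.2.6 and the Part B sentence of Section 12.2.3 both name 100 mL. That gap is editorial.

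**Conclusion.** The point holds as a modest, conditional one. The mechanism follows from the amended protocol: outcome-dependent stopping of active drug, no resiting, and systemic AEs shown only as crude incidence by the period's active volume. If ISR rates differ between volumes, the more irritating one has its systemic AE incidence understated by roughly 0.5 to 2.6 subjects of 32 at an assumed 20% risk over six infusions, and proportionately more or less at other risks. If ISR rates are equal, there is no distortion.

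The size rests on assumed ISR rates, onset times and AE risk, and on AE risk depending on the number of active infusions. The documents do not say that 50 mL will have more ISRs, so it would be wrong to conclude that the table will favour it. The case for acting is that the data are already collected and no other planned summary shows systemic safety by volume in Part A.

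**What to change.** In Section 12.2.3, or in the SAP if there is one:

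1. Keep crude systemic AE incidence by active volume as the main Part A display.
2. Tabulate the number of active infusions and the mg of ceftaroline fosamil received per volunteer, by active volume, from the data recorded under Section 5.5.2.
3. Add a supplementary systemic AE rate per active infusion given, with a note that it assumes constant risk per infusion.
4. Flag in the listing each AE that starts after active infusions stopped in that period.
5. Add 100 mL to the volumes named in the Part A sentence (editorial).

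Do not simply cut AE counts off at 24 hours after the last active infusion without an exposure denominator. That would remove more events from the volume with more early stops and deepen the understatement.

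The cost is analysis wording and one or two extra tables, with no new data and no change to conduct or to the stopping rule. The rate will be imprecise at 24 to 32 volunteers and should be read as context for the crude figures.
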